### 7.1.4 Lot number, Expiry date, Quality control results of study vaccine lots

In 2016, IVAC had produced 3 lots of study vaccine which are 004-01-16, 005-01-16, 006-01-16. These vaccine lots were tested by National Institute for Control of Vaccines and Biologics (NICVB) and met the quality requirement with corresponding certification numbers 00416/VXVR-NC, 00516/VXVR-NC and 00616/VXVR-NC dated 22/12/2016; and one lot of placebo 007P-01-16 was also tested by NICBV with certification number 00716/VXVR-NC dated 29/12/2016.

The vaccine lot number IVACFLU-S 004-01-16 (manufacturing date 29/11/2016, expiration date 05/12/2017) and placebo lot number VACFLU-S 007P-01-16 (manufacturing date 02/12/2016, expiration date 05/12/2017) were used as study materials in this phase 2/3 clinical trial. Details on the test results of these lots are in the [appendix E](#) "Quality certification by NICBV" for the study product lots.

Other detailed information on the 2 study product lots can be found in the Investigator Brochure (IB).

## 7.2 Dosage, Preparation and Administration of Study Products

### 7.2.1 Dosage and Schedule

A single dose level of IVACFLU-S will be evaluated in this study. The dose will be a total of 0.5 mL containing 15 mcg HA for each component. The vaccine is to be delivered intramuscularly preferably into the deltoid of the non-dominant arm.

### 7.2.2 Precautions and Warnings

1. IVACFLU-S is only to be used for adults 18 to 60 years of age participating in this study who meet the inclusion/exclusion criteria. It is forbidden to use the vaccine for any other purpose.
2. Strict compliance with the regulations of the MOH on the use of vaccines and biologicals is required.
3. Vaccination must be intramuscularly preferably into the deltoid of the non-dominant arm.
4. Study product vials that have had any temperature excursions outside the allowable time/temperature enumerated in [section 7.1.3](#), may not be used. Contact IVAC for further instructions.
5. IVACFLU-S or placebo solution is a homogenous preparation, colorless or opaque white. Do not inject if the study product vial appears to have unusual content or if the liquid in the vials has changed color.
6. Only health workers who have been trained and have valid certificate of safe immunization for this research study may administer study product to enrolled participants, assuring proper intramuscular injection technique and sterile injection.
7. Only one person may be injected with one needle and syringe.
8. Study participants must remain in the clinic and be monitored for 30 minutes after vaccination.
9. The study vaccination clinic should have adequate facilities for monitoring and treating any reactions. Drugs to treat anaphylaxis must be available, as must specialist doctors for such an emergency. Prompt referral to additional needed facilities must be available.

### 7.2.3 Preparation and Administration

To prepare and administer study product, vaccination facilities and investigators must comply with current Ministry of Health regulations on vaccination. The step-by-step instructions for the investigator (or delegated staff) are as follows:

- Wash hands or clean hands with hand sanitizer. Prepare the study vaccine/placebo, needles, syringes, and sharps safety box ahead of time.
- Specific study procedures will be developed and include selecting the appropriate vial for each participant, gently shaking the vaccine vial, withdraw the 0.5-mL dose of study vaccine/placebo from the vial using a sterile needle and syringe. Careful records must be maintained to ensure and document that each participant receives the correct dose. Once the dose vial has been penetrated, the withdrawn study vaccine/placebo should be used

promptly.

- Make sure you have sufficient equipment to provide every participant with a safe injection and to dispose of injection materials safely.
- Make sure you have emergency drug and equipment kits in both the vaccination area and the observation area.
- Greet the participant in a friendly manner. Ask whether he/she has any questions or concerns about injection and respond to his/her questions and concerns in a truthful and pleasant manner.
- Confirm the participant identity.
- Ensure the participant is seated.
- Inform the participant that for consistency in the study, all participants will be vaccinated preferably in the deltoid of the non-dominant arm.
- Use the cotton swab with 70^0 alcohol to clean and disinfect the site for injection
- Inject intramuscularly the entire contents of the syringe into the deltoid region of the upper arm.
- While the plunger is still depressed, remove the needle from the participant's arm.
- Apply a dry cotton swab with pressure to the injection site.
- Do not recap the needle. Dispose of the needle and syringe in a sharps container. Store the empty vial in a safe place (not the refrigerator) until the end of the study. The vial must not be disposed of until monitors have verified that it is allowed.
- Record the date of vaccination and vaccine vial number on the participant's vaccination CRF.
- Ask the participant to rest for 30 Minutes.
- While the participant is resting, provide the Diary Card, ruler and thermometer and explain how to use them for recording symptoms. Remind them of upcoming phone calls/visits.
- For 30 Minutes following vaccination, observe the participant and ask about the participant's well-being.
- Before the participant leaves, instruct the participant to seek medical assistance if adverse events occur that require medical evaluation and treatment.

### **7.3 Modification of Study Product for a Participant**

There is no dose adjustment for the product in the study.

### **7.4 Accountability Procedures for Study Product**

The study vaccine and placebo will be kept in a secure place in cold storage (with backup power and/or storage) at the District Health Centers segregated from other products. During the study, the investigator or the person in charge of research product management will record information related to the delivery of vaccine and placebo to the trial site, conduct inventory at the trial site, check the number of doses given to the participants, check the number of unused doses. At the end of the study, the site will receive instruction from the Sponsor regarding the final disposition of any remaining study products.

#### **At the vaccination site**

On scheduled vaccination days, study vaccine and placebo will be kept in the cold boxes with proper temperature control and monitoring.

Standard procedures will be followed at the trial site to maintain proper transport, receipt, storage and return of study products.

In the case of interruptions of the cold chain other than that described in the [section 7.1.3](#) above, the investigator or qualified designated staff member must contact IVAC to get further instructions. The investigator must receive the written consent from IVAC before clinical trial products can be used.

### **7.5 Assessment of Compliance with Use of the Study Products**

Compliance with use of the study products will be closely monitored during the trial by the research team, IVAC and trial monitors.

### **7.6 Concomitant Medications/Treatment**

Concomitant medications for the treatment of pre-existing medical condition, and per AEs / SAEs reporting period outlined in [Table 1](#) and [Section 10.3](#) will be documented throughout the course of the study. Treatment of conditions that are not exclusionary should continue, if needed by the participant. Subsequent changes in concomitant treatment during the trial must also be reflected in the CRF. Women included in the trial who are using hormonal contraception for pregnancy prevention should use these products through Day 22. Use of such products must also be documented in the CRF.

### **7.7 Unauthorized Products**

The following products are not authorized to be used during the study:

1. Any concomitant medicine or biologic specifically prescribed for the treatment of a condition which is an exclusion criterion for participation in the trial.
2. All non-study vaccines or biologics (including blood products). (Can be used after Day 22.)

Other concomitant products are allowed.

Participants will be requested not to take analgesic or antipyretic drugs in a preventive way (before or soon after injection), as such medications might change the reactogenicity profiles of study vaccine and placebo. Participants may take antipyretic drugs after injection, however, to treat a high fever.

If during the trial a situation arises where there is an adverse reaction or AE requiring treatment and prescription of unauthorized products or products not stipulated by the protocol, then such products may be prescribed. However, IVAC must be informed of such an occurrence within 48 hours. Information on the products (trade name, dosing or change in dosing, indications, start date, and termination date) must be recorded in the CRF.

## 8 Study Schedule; Description of Visits

The total duration for this study is approximately 22 months; with approximately 12 months (Sep 2016 to Sep 2017) for preparation and implementation of both phases of the study ; and approximately 10 months for data analysis, CSR completion and review, approval by local IRBs and Ministry of Health. The recruitment and screening is expected to take no more than 3 weeks for phase 2 and 5 weeks for phase 3 study. In both the studies there are 3 scheduled in-clinic visits and one final study visit via telephone.

### The total expected duration of the study:

First participant enrolled in study	D1 of first participant
The last participant enrolled in study	For phase 2: Day 1 of last subject is estimated approximately 3 weeks from Day 1 of first subject For Phase 3: Day 1 of last subject is estimated approximately 4-5 months from Day 1 of first subject from phase 2
The last participant completes the trial	D91 of last participant
Lock database	approximately 4 weeks after D91 of last participant
Clinical trial report	Approximately 5 months from database lock

### 8.1 Screening

Prior to inclusion into the vaccine study, each participant will be screened through medical history interview and general physical examination. Because screening procedures are required to assess eligibility, they will be performed only after a study consent form has been signed. The investigator or designee will record the screening IDs of all participants who enter screening; whether they entered the trial or failed screening, and the reason for screen failure on the screening/enrollment log.

### 8.1.1 Screening and Enrollment/Vaccination (S1/D1)

After assessing understanding and obtaining consent for the study, participants will be screened for eligibility through medical history review and general physical examination. Women of child bearing potential will have a urine pregnancy test. Screening and enrollment/vaccination will occur on the same day (S1/Day 1), although there is a 4-day window allowed, if the participant has second thoughts and needs more time to consider trial participation. If S1 and D1 are conducted separately, a targeted (symptom-based) physical exam with vital signs (heart rate, temperature, blood pressure), urine pregnancy test (for women of child bearing potential only), and brief medical history update will be performed on the day of vaccination (Day 1) to ensure continued eligibility

After participants are consented, the following activities will occur:

1. The participant will be interviewed to collect baseline demographic data
2. A study clinician will interview the participant to collect a detailed medical history.
3. For women with child bearing potential, a urine pregnancy test will be done.
4. A study clinician will perform a general physical examination. Results will be reviewed by study staff and with the participant to confirm eligibility prior to conduct of further procedures. If a person is considered ineligible based on medical history and physical examination, the study clinician will tell the person that he or she is not eligible.
5. **For participants at one site in the phase 3 only:** Prior to administration of study product to 252 participants at the Ben Luc site in the Phase 3, a blood specimen for HAI test will be collected. Specimen collection information must be documented on the CRF. About 5 mLs of blood will be collected. There will be no blood collection in the Phase 2 study.
6. The person performing the injection will confirm that the study product about to be injected is the correct one for this participant.
7. The participant will be administered one injection of study product in the deltoid muscle, preferably the non-dominant arm. (This may be switched to the dominant arm if the participant desires).
8. The participant will be observed for 30 minutes after administration. If the participant experiences an immediate adverse reaction, he/she will be treated and the event will be recorded on the appropriate CRF.
9. The participant will be given a Diary Card, thermometer and ruler in which the participant will be asked to record any local and/or systemic reactions that might appear starting from the evening of Day 1 to Day 7. Concomitant medications and other AEs may be recorded on the Dairy Card, too. The participant will be instructed how to use the Diary Card, thermometer and ruler. All relevant explanations should be included in the Diary Card. The Diary Card will also have contact information for the investigators, should the

participant have any questions. The participant will be informed that a member of the investigator's team will visit the participant the next 24 hours (Day 2) in phase 2 and visit/call in phase 3 and also call her/him 4 days (Day 5) after vaccination to check on the participant's completion of the Dairy Card and participant's well-being.

10. The participant will be instructed that if the participant experiences an AE requiring medical care, the participant should inform the investigator as soon as possible and seek medical care as appropriate. If the participant visits a health care provider, the participant should be sure to inform the health care provider of participation in this study and provide the health care provider with the investigator's contact information.

## **8.2 Follow-up Periods**

### **8.2.1 First Week after Injection (Days 1 to 7)**

1. The participant will complete the Diary Card daily, starting on the evening reporting any local or systemic reactions experienced and medications taken.
2. The participant will have been instructed that if he/she experiences an AE requiring medical care, the participant should inform the investigator as soon as possible and seek medical care as appropriate. If the participant visits a health care provider, the participant should be sure to inform the health care provider of participation in this study and provide the health care provider with the investigator's contact information. The participant should obtain in writing the names of medications prescribed by the health care provider.
3. One day after vaccination (Day 2) a member of the investigator's clinical team will visit the participant in phase 2 and visit/call in phase 3 and also call on 4 days (Day 5) to check that the participant is correctly completing the Diary Card and to check on the participant's well-being. If local and systemic reactions suspected to be Grade 3 or higher are reported, the participant will be requested to return to the study clinic for evaluation.

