### **8.2.2 Seventh Day after Injection (Day 8 ± 1)**

1. Study staff will confirm participant identity.
2. Study staff will review the participant Diary Card and interim history with the participant and inquire about any new medical events since medical histories were last updated. Any AEs that have occurred and meet reporting requirements, will be recorded in the appropriate section(s) of the CRF. Diary Card information will be entered into the database.
3. The participant will have temperature, pulse rate, and blood pressure recorded. A study clinician will perform a targeted (symptom based) physical examination and record the information Results will be reviewed by study staff and with the participant.
4. The participant will be instructed to inform the investigator as soon as possible if he/she experiences an AE requiring medical care and to seek medical care as appropriate. If the participant visits a health care provider, the participant should be sure to inform the

health care provider of participation in this study and give the health care provider the contact information for the investigator.

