#### 10.1.1 Solicited Local and Systemic Adverse Events

- Solicited adverse events are pre-specific local and systemic adverse events that are common or known to be associated with vaccination that are actively monitored as indicators of vaccine reactogenicity. Investigators will not be required to assess causality of solicited adverse events if the onset is during the solicitation periods. If a solicited adverse event progresses beyond the solicited period, it will continue to be reported as a solicited adverse event. If the solicited adverse event occurs after the solicitation period it will be reported as an unsolicited AE.
- For this trial, solicited local and systemic AEs will be assessed by study staff 30 minutes after vaccination then daily for 7 days by the participants. Participants will be provided a thermometer, ruler and a diary to record the presence or absence of solicited AEs, severity of the solicited AE and use of concomitant medication. The severity of the solicited local and systemic adverse events will be graded using the Toxicity Table for Grading Adverse Events ([Appendix A](#)). The specific solicited local and systemic adverse events that will be reported for this trial are:
  - **Solicited local adverse event (at site of injection):**
    - Erythema / redness – based on size in cm
    - Swelling / induration (hardness at site of injection ) – based on size in cm
    - Pain

- **Systemic Reactions:**

- Fever--Body temperature
- Fatigue/malaise
- Generalized muscle aches
- Joint aches
- Chills
- Nausea
- Vomiting
- Headache

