**TAKE-HOME DIARY CARD**

**Other COMPLAINT or ILLNESS:**  
 Did you have any other things that bothered you?     Yes     No  
 Record any other complaints or illness which developed or worsened during the 7-day follow-up period after receiving the study injection.  
 List each illness or complaint separately.  
 You may call study doctor for any other complaints or illness.

Complaint or illness	Start date	Last day the illness or complaint presents (*)
Example: Cough	21/07/2017	23/07/2017
1.		
2.		
3.		
4.		
5.		

(\*) Write “**continuing**” if the illness is still going on day 7.

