## 12. MEDICATIONS

Medications will be presented for the FA population and are not coded.

Frequency and percentage of subjects receiving concomitant medications will be summarized by vaccine and placebo for each reported term.

A subject will be counted only once under reported term if the subject receives same concomitant medication multiple times.

By-subject listing of the data will be presented for the FA population.

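### The protocol makes the diary the record of medicines taken in Days 1-7, but the supplied card has no medicine field and no visit step asks about medicines before Day 22

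*Combined protocol and SAP*

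**What the plan says.** Two protocol sections give the diary the job of recording medicines. Section 8.2.1 (first week after injection) states: "The participant will complete the Diary Card daily, starting on the evening reporting any local or systemic reactions experienced and medications taken". Section 10.1.1 gives participants a diary to "record the presence or absence of solicited AEs, severity of the solicited AE and use of concomitant medication". Section 8.1.1 item 9 is weaker: it says only that concomitant medications may be entered on the card.

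Section 7.7 explains why the first week matters. It asks participants not to take analgesics or antipyretics preventively, "as such medications might change the reactogenicity profiles of study vaccine and placebo", and it allows antipyretics to treat a high fever.

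At Day 8 (8.2.2) the instruction is: "Study staff will review the participant Diary Card and interim history with the participant and inquire about any new medical events". Medicines are not named.

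The only free-entry page of the take-home card reads: "Record any other complaints or illness which developed or worsened during the 7-day follow-up period after receiving the study injection". Its columns are the complaint, its start date and its last day.

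SAP section 12 says of these data: "Medications will be presented for the FA population and are not coded". They are summarised by arm for each reported term.

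**The concern.** Solicited local and systemic events over Days 1-7 are primary safety endpoints (protocol 3.2.1) and are compared between arms by Fisher's exact or Cochran-Mantel-Haenszel test (protocol 13.7, SAP 17.2.1). The protocol itself regards preventive analgesic or antipyretic use as able to alter those results. To judge whether participants kept to the 7.7 request, or how much treatment use there was in each arm, one needs dated medicine records from the same seven days. The protocol names the diary as the source of those records, yet the card cannot hold them. A site that follows both documents exactly would reach Day 22 with no written participant record of medicines and no instruction to ask for one.

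**Working it through.** The plan states no figure here. The check sets the passages side by side.

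1. **What the diary is meant to hold.** 8.2.1: daily medicines. 10.1.1: use of concomitant medication. 8.1.1 item 9: medicines permitted, and all relevant explanations to be on the card. The diary row of Table 1 mentions only reactogenicity and unsolicited events, and Table 1 has no medication row.

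2. **What the supplied card holds.** Its instructions cover temperature, measurement of the injection site and severity. Its pages cover oral temperature, pain, tenderness, redness, swelling, hardness, seven systemic symptoms and other complaints. Neither mentions medicines. The card is Version 1, dated 14 December 2016, whereas the SAP is based on protocol version 4.0, dated 09 February 2017.

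3. **What staff are told to ask, in time order.**
- Day 2 and Day 5 contacts (8.2.1 item 3): diary completion and well-being. The eCRF contact form holds a date and whether the participant was reached.
- Day 8 (8.2.2): diary, interim history and new medical events. The Day 8 solicited reactogenicity forms have no medicine item.
- Day 22 (8.2.4): interim histories and concomitant medications. This is the first post-vaccination visit step to name medicines.

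4. **Recall interval if Day 22 is the first time anyone asks.** The visit window is ±1 day. Shortest: use on Day 7, asked on Day 21, 21 − 7 = 14 days. Longest: use on Day 1, asked on Day 23, 23 − 1 = 22 days.

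5. **Where the data would go.** The eCRF log asks whether any concomitant medication was reported. A yes leads to a repeating form with start and stop dates and an indication that can be a solicited AE, itemised by symptom. Neither item is scheduled at Day 8. The date fields accept an unknown day or month, so a recalled medicine could be entered without being placeable in Days 1-7. Preventive use has no solicited AE as its indication and would be found only by date or free text.

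6. **What the SAP shows.** Shell Table 14.1.3.1 has a row for at least one medication and then rows by reported term. It has no Day 1-7 window and no analgesic or antipyretic row, and one medicine reported under two trade names would occupy two rows. Listing 16.2.4.3 gives treatment, dates, study day and indication by subject.

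**The case against.** The strongest reply is that capture does not depend on the diary. Section 7.6 requires medication to be documented throughout the study. The log question and the dated medication form exist, with an indication built for solicited reactions. Staff review adverse events with the participant at Day 8, and the eCRF local reactogenicity form is completed from memory aids and interview. Participants are told to obtain in writing the names of medicines that a provider prescribes. The Day 22 wording, which updates medications since the last update, presupposes that earlier updates can occur. By-arm tabulation and a dated listing are already planned. No analysis adjusts for covariates (SAP 7.1), so no planned test uses medication.

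Most of this stands. It rules out the inference that first-week medicines go unrecorded, or that the trial cannot show use by arm. It does not supply the missing prompt. The eCRF form is a destination, not a source; 7.6 does not say when to ask; and provider prescriptions leave out medicines that participants buy themselves.

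A reader might also infer that under-recorded use is concentrated in the vaccine arm and pulls the arm difference towards zero. The documents do not support that. Section 7.7 says only that preventive use might change the profile; extending it to treatment of a reaction is inference, and later treatment does not erase a reaction already recorded. The apparent size depends on the Phase 1 rate chosen. Assume, without support in the documents, that 10-30% of participants with a reaction take such a medicine:
- Day 1 local rates: 0.667 × 0.10 to 0.30 = 6.7-20.0% on vaccine (about 49-148 of 740), and 0.267 × 0.10 to 0.30 = 2.7-8.0% on placebo (about 4-12 of 148). The ratio of 2.5 is just 66.7/26.7.
- Day 1 systemic rates: 2.7-8.0% on vaccine (about 20-59 of 740) and 2.3-7.0% on placebo (about 3-10 of 148). The ratio is 26.7/23.3 = 1.15 from the rounded rates.

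Phase 1 had 30 participants per arm and no fever, and headache over Days 1-7 was reported by 7 on vaccine and 9 on placebo.

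Nor is it a fault that the card ends at Day 7. The protocol promises no longer diary, and the card refers to a separate form for symptoms continuing after that day.

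**Conclusion.** The mismatch is real and should be reconciled. Sections 8.2.1 and 10.1.1 rely on a record that the supplied card cannot provide, and no visit step names medicines until Day 22. Entry on the eCRF before then depends on unprompted interview or recall. Analgesic and antipyretic use in the reactogenicity window, including the preventive use that 7.7 discourages, may therefore be incompletely captured. If nobody asks until Day 22, recall spans 14 to 22 days. The effect on the solicited-event comparison cannot be sized or signed from the documents. This is a low-cost improvement to data collection and reporting; it does not invalidate the safety analysis.

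The conclusion assumes that the supplied card pages are the whole card and that no site worksheet asks about medicines. Some pages are absent from the public file. The appendix list places an eCRF approval form straight after the card, so a missing medicine page is unlikely, but it cannot be excluded.

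**What to change.** 1. Add a daily row to the diary card for any medicine taken, with its name and the reason, and add concomitant medications to the Day 8 review in 8.2.2.

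2. In SAP section 12, have analgesics and antipyretics flagged by blinded review of the reported terms before unblinding. Tabulate by arm the participants with any such use in Days 1-7, with exact 95% confidence intervals, from the existing medication dates and solicited-AE indication. Select on dates as well as indication so that preventive use is counted, and state how entries with a partial date are handled.

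3. Where the supplied card was used, say in the report that Day 1-7 medication was obtained by recall.

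The cost is a reprinted card, one phrase in 8.2.2, one extra table and a small recording burden for participants. If collection is already complete, items 2 and 3 remain feasible without new data.
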